Overview: We will conduct an open-label, randomized controlled trial to assess the effectiveness and safety of treating iron-deficiency anemia in pregnant women with intravenous iron compared with oral iron. We test the *hypothesis* that treating iron-deficiency anemia with intravenous iron is associated with improved maternal and neonatal outcomes compared with oral iron. We will use broad inclusion criteria and analyze data using the intention-to-treat principle to increase generalizability of the findings.

Inclusion & exclusion criteria:

Inclusion criteria:

- Pregnant women
- 18 years or older
- Diagnosed with iron-deficiency anemia
 - Serum ferritin <30ug
 - o Hgb <10 g/dl
- Between 24 34 weeks gestation
- Plan to deliver at an in-network hospital
- Able and willing to give informed consent

Exclusion criteria:

- Diagnosis of non-iron-deficiency anemia
- Multiple gestation
- Known or suspected major fetal anomaly or aneuploidy
- Planned delivery at out-of-network hospital
- Unable or unwilling to give consent

Study outcomes:

Primary outcome: The primary outcome of the trial is maternal anemia, defined as Hgb <11mg/dl, on admission for labor and delivery.

Secondary outcomes:

- 1. Safety:
 - i. Mild/moderate infusion reactions: chest tightness, itching, urticaria, flushing, nausea/vomiting, arthralgia, back or joint aches, mild shortness of breath, tachycardia, hypertension or hypotension, abdominal pain, diarrhea, peripheral edema, headache, dizziness, syncope, or numbness.
 - ii. Major infusion reaction: anaphylaxis-like reaction, seizures, or non-reassuring fetal heart rate tracing.

2. Maternal outcomes:

- i. Hgb at admission to labor and delivery
- ii. Hgb on postpartum day 1
- iii. Ferritin at admission to labor and delivery
- iv. blood transfusion
- v. mode of delivery
- vi. postpartum disposition
- vii. readmission

3. Neonatal outcomes

- i. gestational age at delivery
- ii. birth weight
- iii. cord gases (if performed as SOC)
- iv. umbilical artery lactate (if performed as SOC)
- v. APGAR scores
- vi. Hgb (obtained from cord blood)
- vii. Ferritin (obtained from cord blood)
- viii. neonatal morbidities
- ix. postpartum disposition

Screening:

[figure not shown]

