Pregnant women attending prenatal care will be screened for anemia with repeat CBC at 24 to 28 weeks gestation per standard of care. If the initial Hgb at this gestational age is less than 10 mg/dL, they will undergo testing for iron-deficiency anemia. Iron-deficiency anemia will be defined as anemia with serum ferritin <30ug. Any pregnant woman diagnosed with iron-deficiency anemia who meets all inclusion criteria and no exclusion criteria will be eligible for the study (**Figure 1**). In addition, patients who present for prenatal care after 28 weeks gestation who meet all inclusion criteria and no exclusion criteria will be eligible for enrollment if they are diagnosed with iron-deficiency anemia prior to 34 weeks.

Randomization and Treatment Groups: Patients meeting all inclusion criteria and no exclusion criteria who sign informed consent will be enrolled and randomly assigned in a 1:1 ratio using a computer-generated randomization sequence to one of two treatment protocols. The two treatment protocols are:

- 1. Oral Iron Supplement- Oral iron supplementation will occur throughout pregnancy with ferrous sulfate at a dose range of 325mg daily to 325mg three times daily. Patients will be instructed to take on an empty stomach or with an acidic beverage like orange juice. Patients will continue oral iron supplementation through delivery, then refer to their treating physician for further postpartum consumption. Patients will be asked to report any side effects of oral iron between 2 4 weeks after randomization. Side effects will also be assessed at delivery along with reported compliance to the oral iron regimen.
- 2. Intravenous Iron- The intravenous iron infusion will occur in the form of 975mg of intravenous iron dextran diluted in 250 or 500mL of 0.9% sodium chloride given as a single dose over 1-2 hours. Prior to starting the treatment dose, participants will receive a test dose of 0.5mL (25mg) of iron dextran and will be monitored by hospital nursing staff for 20-30 minutes (or per local infusion protocol) to ensure there are no transfusion IVIDA.Version [6.2] 09.18.2019

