reactions. This amounts to a cumulative dose of 1000mg IV iron dextran. If iron dextran is unavailable due to drug shortage, ferumoxytol will be substituted for this treatment group. Subjects will be given an initial 510mg IV dose in 100 ml 0.9% sodium chloride over at least 15 minutes. This dose will be followed by a second dose of the same concentration 3 to 8 days later. All iron infusions will occur on an obstetric unit equipped with continuous monitoring and emergency equipment. Patients will have continuous fetal monitoring throughout and at least 30 minutes after the infusion. Patients will be called by research staff 48 - 72 hours after infusion (second infusion if administering ferumoxytol) to assess for transfusion reactions. Women who receive intravenous iron will not receive further oral iron supplementation during pregnancy. Postpartum iron supplementation will be left to provider discretion.

Figure 1: Study protocol

^{*}If iron dextran is unavailable due to drug shortage, ferumoxytol will be substituted. The initial dose will be 510mg ferumoxytol IV followed by a second dose of 510mg ferumoxytol IV 3 to 8 days later.

STUDY PROCEDURES

Study patients will have hemoglobin drawn at admission to labor and delivery and on postpartum day one. Neonatal hemoglobin and ferritin (and blood gases and/or lactate if performed out of clinical necessity) will be assessed via cord blood. Obstetric and neonatal outcomes will be collected by a trained research nurse. Subjects randomized to the oral iron group will be asked to report compliance with taking oral iron supplements as well as any side effects of taking the oral iron. This self-report will be assessed during their admission to labor and delivery (or via phone up to 2 days after discharge). See **Figure 2** for schedule of events. Pregnancy, labor and delivery management will be per standard obstetric practice.

Figure 2: Schedule of events

Event	Screening & Enrollment 24-34 weeks	Prenatal Period	48-72 hrs after infusion*	Delivery	Postpartum period prior to discharge
Inclusion/Exclusion	Х				
Informed Consent	X				
Demographics	X				
Prenatal history	X				
Randomization to oral iron vs. IV iron	Х	Oral continues Infusion occurs*			
Phone call: AEs/ outcomes of IV iron			Х		
Effects & outcomes of oral iron supplementation (self-report)		X (Once 2-4 weeks after randomization)		х	
Oral iron compliance (self-report)				х	
Maternal blood draw: Hgb	SOC			х	X PPD1

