- venipuncture complications (blood clot or infection)
- o bowel changes (constipation or diarrhea)
- chest tightness
- itching
- o urticaria
- flushing
- o nausea/vomiting
- o abdominal pain
- o peripheral edema
- arthralgia
- o new onset back or joint aches
- o mild shortness of breath
- tachycardia
- o severe hypertension (For infusion group: confined to infusion timeframe only)
- o severe hypotension (For infusion group: confined to infusion timeframe only)
- o neurological changes (syncope, dizziness, headache) (For infusion group: confined to infusion timeframe only)

Major reactions:

- o anaphylaxis-like reaction (For infusion group: confined to infusion timeframe only)
- o seizures (For infusion group: confined to infusion timeframe only)
- o non-reassuring fetal heart rate tracing (For infusion group: confined to infusion timeframe only)

Assessing and Documenting Reportable Events:

Subjects will be evaluated for adverse events in the following manner:

- Routine monitoring by infusion nurses during the IV iron treatment, with data obtained from the subject's EMR by research staff.
- Subjects will be called by research staff 48-72 hours after infusion to assess for transfusion reactions.
- Subjects on oral iron therapy will be monitored via their EMR and via contact with research staff as outlined in schedule of events

An adverse event report will be generated for each event that will include the following:

- Date of event discovery
- Severity (mild, moderate, severe, life threatening/disabling, death)
- Relationship to treatment
- Action taken
- Outcome
- Expected or not
- Date reported
- Relevant notes/chart records/supporting documentation to corroborate the event
- To whom event was reported (i.e. IRB, lead site, etc.)
 - Non- serious AESIs will be reported to the lead site within 5 days of discovery, and to the IRB at renewal.
 - SAEs and SAESIs will be reported within 24 hours of discovery to the IRB and the lead site.

Relationship of Reportable Events:

An investigator must make the determination of relationship to the drug for each SAE and/or AESI. The relationship to the drug should be assessed using the guidelines presented in the table below.

Relationship to Drug	Description
Related	Previously known toxicity of agent; or
	 Follows a reasonable temporal sequence from administration of the drug; or
	• Follows a known or expected response pattern to the suspected intervention; or

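### The infusion-reaction outcome has no new-or-worse rule and no scheduled pre-treatment symptom record, so existing complaints may be misclassified as reactions

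*Combined protocol and SAP*

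**What the plan says.** **Outcome definition.** Safety is the first secondary outcome under Study outcomes. Mild/moderate infusion reactions are given as a list: "chest tightness, itching, urticaria, flushing, nausea/vomiting, arthralgia, back or joint aches, mild shortness of breath, tachycardia, hypertension or hypotension, abdominal pain", followed by diarrhea, peripheral edema, headache, dizziness, syncope and numbness. A major reaction is "anaphylaxis-like reaction, seizures, or non-reassuring fetal heart rate tracing". Neither definition mentions onset, change from a prior state, or relatedness.

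**Before treatment.** The screening column of Figure 2 holds eligibility, consent, demographics, "Prenatal history", randomization, and standard-of-care hemoglobin and ferritin. It has no row for symptoms, vital signs or a fetal tracing.

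**After treatment starts.** In the IV arm, under Randomization and Treatment Groups, women given the iron dextran test dose "will be monitored by hospital nursing staff for 20-30 minutes (or per local infusion protocol". The same section says: "Patients will have continuous fetal monitoring throughout and at least 30 minutes after the infusion". Findings from the infusion nurses' routine monitoring are taken from the medical record (Assessing and Documenting Reportable Events). Research staff then telephone at 48-72 hours, the Figure 2 row "Phone call: AEs/ outcomes of IV iron". In the oral arm, side effects are self-reported 2-4 weeks after randomization and again at delivery.

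**AESI section.** This list is narrower in places. Aches count only as "new onset back or joint aches", and blood-pressure events must be severe. For the infusion group, blood-pressure, neurological and major events are limited to the period of the infusion. The investigator must grade the relationship of every SAE and AESI to the drug.

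**The concern.** The outcome is called an infusion reaction, but what defines it is the presence of a symptom or sign. Several listed items are non-specific, and the protocol itself gives reasons to expect some of them before treatment. Prior oral iron is not an exclusion, and Potential Risks lists nausea/vomiting and stomach discomfort as common with oral iron and diarrhea as less common. Nausea/vomiting, abdominal pain and diarrhea are also listed infusion reactions. Hypertension is not an exclusion either, yet it appears unqualified in the outcome list.

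Safety is half of the stated objective, and the Background cites insufficient data on adverse effects as part of the reason for the trial. In an open-label study, whether a complaint predates the drug would be settled afterwards, by staff who know the assignment, from recall and whatever the chart contains. A baseline that was never recorded cannot be reliably recovered later.

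**Working it through.** The plan gives no reaction rate or background symptom prevalence, so there is no figure of its own to reproduce on this point. The check is a comparison of the two lists, followed by a labelled illustration.

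**1. The two lists side by side**

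| Item | Study outcomes | AESI list |
|---|---|---|
| Back or joint aches | unqualified | new onset required |
| Hypertension, hypotension | unqualified | severe only; infusion period only (infusion group) |
| Headache, dizziness, syncope | unqualified | infusion period only (infusion group) |
| Anaphylaxis-like reaction, seizures, non-reassuring tracing | unqualified | infusion period only (infusion group) |
| Nausea/vomiting, itching, mild shortness of breath, tachycardia, peripheral edema, abdominal pain | unqualified | unqualified |
| Numbness | listed | absent |

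So the limits that exist sit only in the AESI list, and the fifth row has no onset or timeframe limit in either place. The mismatch also affects data capture. The Adverse Events section says that, among AEs, only AESIs go on the CRF. Numbness and non-severe blood-pressure changes are therefore part of the outcome but have no stated route onto the form, unless they qualify as SAEs.

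**2. Could anything already planned serve as the baseline?**
- Prenatal history is collected, but its content is not specified.
- The 20-30 minute nursing observation follows the 25 mg test dose, so it is not an untreated baseline.
- Fetal monitoring is stated for the infusion and at least 30 minutes afterwards; no preceding period is stated.
- An infusion-period limit restricts when a finding is seen. It does not show that the finding was absent before.
- The relatedness scale weighs the woman's clinical state, but neither Study outcomes nor Data analysis says which grades count toward the outcome.

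**3. Worst-case illustration**

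Inputs:
- n = 60 in the IV arm, from 120 recruited at 1:1 (Sample size estimation; Randomization and Treatment Groups).
- t = true reaction rate, and b = proportion with at least one listed complaint beforehand. Both are assumed, because the documents give neither.
- Every existing complaint is counted and is independent of true reactions.

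Recorded rate = 1 - (1 - t)(1 - b). For t = 5% and b = 10%: 1 - 0.95 × 0.90 = 14.5%, and 60 × 0.145 = 8.7 women, against 60 × 0.05 = 3.0 true reactions.

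| t | b = 10% | b = 20% | b = 30% |
|---|---|---|---|
| 2% (1.2 women) | 11.8% (7.1) | 21.6% (13.0) | 31.4% (18.8) |
| 5% (3.0 women) | 14.5% (8.7) | 24.0% (14.4) | 33.5% (20.1) |
| 10% (6.0 women) | 19.0% (11.4) | 28.0% (16.8) | 37.0% (22.2) |

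The AESI limits and relatedness grading would screen out some of these. To allow for that, read b as the proportion of women whose existing complaint still gets through and is counted. At b = 5% and t = 5%, the recorded rate is 1 - 0.95 × 0.95 = 9.8%, or 5.9 women. At b = 0 there is no inflation.

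**4. Primary outcome**

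The sample size does not depend on any of this. With the unpooled normal approximation, (1.960 + 0.842)² × (0.385 × 0.615 + 0.154 × 0.846) / 0.231² = 53.99, so 54 per arm and 108 in total; 108 / 0.90 = 120, as stated.

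**The case against.** The strongest reply is that the plan nowhere says existing complaints count. The outcome is named a reaction, and an AE is defined by its timing relative to the product. Every AESI is graded for relationship on a scale that includes unlikely and not related. Six AESI lines are limited to the infusion period for the infusion group, including headache, dizziness and non-reassuring tracing. The words for bowel and neurological items speak of changes, which suggests departure from a prior state. The telephone call is made to assess for reactions, and oral-arm women are asked about side effects of oral iron, so both enquiries already invite attribution.

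Much of this stands. A reader might infer that pre-existing complaints are counted as reactions. The documents do not support that: they neither include nor exclude them, so this is a risk of misclassification only. A reader might also infer that IV-arm symptoms are first looked for at 48-72 hours. That is wrong as well, because nurses observe women after the test dose and during the infusion. The call is the first scheduled enquiry by research staff.

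The reply does not close the gap. The limits are absent from the outcome definition, the unqualified items remain unqualified in both lists, and the relatedness grade is not tied to the outcome and has no recorded baseline to rest on. The oral arm is a lesser matter: the outcome under Study outcomes covers infusion reactions only, and the same question arises there only for the AESIs.

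**Conclusion.** The point holds as a gap in definition and measurement. The infusion-reaction outcome has no treatment-emergent rule, no pre-treatment symptom or vital-sign record is scheduled in either arm, and the outcome and AESI lists do not match.

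The size cannot be determined from the documents. The range of 14.5% to 33.5% recorded for an assumed true 5% rests on three assumptions: prior prevalence of 10% to 30%, independence, and every existing complaint being counted. It is a worst case, and reading it as an estimate of bias in this trial would go beyond the documents. That such complaints are frequent in this population is plausible, but no prevalence is given.

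Only a secondary safety outcome is affected; the primary outcome and sample size are untouched. The change is still worth making, because it is cheap and the missing information cannot be collected afterwards.

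**What to change.** - Add a Figure 2 row: complete the AESI checklist at randomization in both arms, and again in the IV arm just before the first infusion (before the test dose where one is given). At the second point, record the vital signs and any fetal tracing already available on the unit. No new monitoring procedure needs to be mandated for this.
- Define the infusion-reaction outcome under Study outcomes, and the AESIs, as symptoms or findings that are new or worse than that baseline.
- Reconcile the two lists. Decide whether the blood-pressure severity limit and the infusion-period limits apply to the outcome, and whether numbness belongs in both lists, so that everything in the outcome is captured on the eCRF.

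The cost is a few minutes per participant and a small protocol and eCRF amendment, with no extra visit.

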Potential Risks: Patients participating in this study who undergo oral or intravenous iron supplementation are at risk for the following:

- Low Risk
 - Blood draw complications:
 - Common: minor pain at site, bruising
 - Less common: fainting or dizziness
 - Rare: blood clots or infection at IV site
 - Breach of confidentiality
- Moderate/High Risk
 - Oral iron supplement side effects:
 - Common: constipation, nausea/vomiting, stomach discomfort or upset, dark stools
 - Less common: diarrhea, heartburn, urine discoloration
 - Iron dextran and ferumoxytol infusion side effects:
 - Common: discomfort and/or bruising at the IV site
 - Less common: chest tightness, itching, urticaria, flushing, nausea/vomiting, arthralgia, back or joint aches, shortness of breath, tachycardia, hypertension or hypotension, abdominal pain, diarrhea, peripheral edema, headache, dizziness, syncope, or numbness.
 - Rare: Anaphylaxis, seizures, or non-reassuring fetal status

Protections Against Risks

Subjects eligible for recruitment will be approached in a private clinic location. The informed consent process and every study visit will occur in a private location. Every follow up interview will be conducted in a private setting, or it can be conducted over the phone if the participant would prefer that option. Prior to beginning any phone interviews, study staff will ensure that the participant is in a private space.

The measures outlined below will be employed to monitor and minimize risks.

- i. Patients will be counseled about the risks prior to enrollment in the study.
- ii. Patient confidentiality will be protected by ensuring only research personnel have access to identifiable patient information. Study files will be kept in a secure room. Patient information will be coded and deidentified prior to analysis and publication of study results.
- iii. All iron infusions will occur on an obstetrics unit equipped with emergency protocols and equipment in the rare event that a serious adverse event may occur and/or emergent delivery is necessary. All subjects will be infused with close monitoring including continuous fetal heart rate tracing. If an infusion reaction occurs at the time of infusion, treatment will be administered per the unit care team.
- iv. Patients will be contacted by phone by research staff 48 72 hours after infusion to assess for transfusion reactions.

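### Neither written exclusion list addresses a known serious reaction to the study intravenous iron products, so a woman with such a history could be randomized to them

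*Combined protocol and SAP*

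**What the plan says.** The exclusion criteria appear twice, in the Synopsis and under Inclusion & exclusion criteria in Study Design and Methods, with the same five items. In the second list they are "Diagnosis of non-iron-deficiency anemia", multiple gestation, "Known or suspected major fetal anomaly or aneuploidy", planned delivery outside the network, and "Unable or unwilling to give consent". The inclusion criteria cover pregnancy, age, ferritin and hemoglobin, gestational age, delivery hospital and consent. No item in either direction asks whether the woman can be given the study drugs.

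Screening then makes the lists sufficient: "Any pregnant woman diagnosed with iron-deficiency anemia who meets all inclusion criteria and no exclusion criteria will be eligible for the study". Under Randomization and Treatment Groups, women who consent are "randomly assigned in a 1:1 ratio using a computer-generated randomization sequence to one of two treatment protocols".

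The IV arm is planned around iron dextran, with a fallback: "If iron dextran is unavailable due to drug shortage, ferumoxytol will be substituted for this treatment group". Potential Risks, in Human Subjects Protection, covers both products in one entry that ends "Rare: Anaphylaxis, seizures, or non-reassuring fetal status". Study outcomes lists an anaphylaxis-like reaction first among the major infusion reactions.

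Data analysis keeps each woman in her randomized group whether or not she was treated as assigned. The IV paragraph bars further oral iron only for women who receive the infusion.

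**The concern.** The protocol recognizes a severe reaction to IV iron as a hazard and builds a test dose, emergency equipment and fetal monitoring around it. It does not use the one piece of information available before randomization that bears directly on that hazard, namely a known earlier reaction. Take, for illustration, a woman with hemoglobin 9.0 g/dl, ferritin 10 and documented anaphylaxis to a previous iron infusion. She meets the laboratory criteria, and her history triggers no exclusion.

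If she is assigned to IV iron, one of two things follows. She may be infused, which puts mother and fetus at a risk that could have been identified at screening. Or the unit may decline, in which case she stays in the IV arm for analysis with her actual treatment undefined by the protocol. Not randomizing her would avoid both.

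**Working it through.** **Step 1. Compare the eligibility lists with the listed risks.**

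| Place | Content | Covers a known reaction to IV iron? |
|---|---|---|
| Synopsis, exclusion criteria | Five items | No |
| Study Design and Methods, exclusion criteria | The same five items | No |
| Both inclusion lists | Pregnancy, age, laboratory values, gestation, hospital, consent | No |
| Figure 2, schedule of events | Inclusion/exclusion check and prenatal history at enrollment | No separate allergy check; the check applies the lists above |
| Potential Risks | Anaphylaxis listed as rare for both IV products | Names the hazard, sets no rule |

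The exclusion for other types of anemia does not reach this woman, because her anemia is iron-deficient.

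**Step 2. Ask whether an existing safeguard acts as an eligibility rule.** Counseling and consent inform a decision but set no uniform criterion. The monitored unit responds to a reaction once it has begun. The test dose detects a reaction only after exposure, and it is described for iron dextran alone; none is described for ferumoxytol.

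**Step 3. Number of women.** The documents give no frequency, so I assume a range *f* for a prior serious reaction among enrolled women. With 1:1 allocation, 60 of 120 go to IV iron. Expected numbers are 120*f* enrolled and 60*f* in the IV arm. The chance of at least one in the IV arm is 1 − (1 − *f*)^60.

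| Assumed *f* | Expected among 120 | Expected in IV arm | Chance of at least one in IV arm |
|---|---|---|---|
| 0.1% | 0.12 | 0.06 | 5.8% |
| 0.5% | 0.6 | 0.3 | 26.0% |
| 1% | 1.2 | 0.6 | 45.3% |
| 2% | 2.4 | 1.2 | 70.2% |

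**Step 4. Effect on power.** First, the plan's own figure. Inputs from Sample size estimation: 38.5% against 15.4%, 80% power, two-sided alpha 0.05. With unpooled variance,

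n per arm = (1.96 + 0.8416)² × [0.385 × 0.615 + 0.154 × 0.846] / (0.385 − 0.154)² = 7.849 × 0.36706 / 0.05336 = 53.99, so 54 per arm and 108 in total. Then 108 / 0.90 = 120.

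This formula reproduces all six values of N in Table 1, so I use it for the rest.

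Now let *k* of the 54 evaluable IV women go uninfused and have anemia rate *r*. The IV-arm rate becomes [0.154(54 − *k*) + *rk*] / 54. For *k* = 1 and *r* = 0.385 it is (8.162 + 0.385) / 54 = 0.1583, and the power is Φ(0.2267 / 0.0828 − 1.96) = 78.2%.

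| *k* | Power if *r* = 38.5% (control rate) | Power if *r* = 100% (extreme) |
|---|---|---|
| 0 | 80.0% | 80.0% |
| 1 | 78.2% | 73.1% |
| 2 | 76.3% | 65.4% |
| 3 | 74.4% | 57.3% |

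The last column is a bound: it requires every uninfused woman to be anemic at delivery, which nothing in the documents suggests. By Step 3, *k* is most likely 0 or 1.

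**The case against.** The strongest defense is that eligibility does not compel infusion. Prenatal history is collected at enrollment, women are counseled about risks beforehand and must consent, and infusion takes place on an obstetric unit equipped for emergencies. A clinician aware of the history would very likely not proceed. The plan also states a pragmatic aim: "We will use broad inclusion criteria and analyze data using the intention-to-treat principle to increase generalizability of the findings". The number affected may be zero. All of this stands as mitigation. None of it is a criterion applied uniformly before randomization, and generalizability is not served by enrolling a woman who may be unable to receive one of the two treatments.

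A reader might infer four stronger things that the documents do not support:

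- *That anaphylaxis is the main risk of IV iron.* Potential Risks classes it as rare; the common effects are discomfort and bruising at the IV site. It is one of three listed major reactions.
- *That an uninfused woman would go untreated.* Oral iron is barred only for women who receive the infusion. The documents are silent on a woman assigned to it but not infused.
- *That the trial knowingly exposes such women.* The history and counseling steps make that too strong. The lists merely fail to exclude them.
- *That the primary comparison is materially diluted.* One such woman at the control rate costs about 1.8 percentage points of power, and intention to treat accepts non-receipt by design.

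One limit on certainty remains. Screening refers to Figure 1, which is not reproduced in the text available for review. Absence from both written lists is certain; absence from every part of the plan is not.

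**Conclusion.** The gap is real. Both written exclusion lists omit a known serious reaction to the study IV iron products, the Screening text makes those lists sufficient, and allocation is 1:1. The plan's other safeguards lower the risk without closing the gap, and the treatment of a woman assigned to IV iron but not infused is left open.

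The importance lies in safety and eligibility. The potential harm is severe and can be identified before randomization, but it concerns few women: 0.06 to 1.2 expected in the IV arm under my assumed frequencies of 0.1% to 2%, and possibly none. The effect on the primary analysis is negligible under the control-rate assumption. The change should be made because it is cheap and prevents a foreseeable hazard; the trial's efficacy conclusion does not depend on it.

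**What to change.** Reconcile both exclusion lists with the infusion risks in Human Subjects Protection by adding an eligibility item on known hypersensitivity to the study iron products. The sponsor should set its clinical content. It should cover the substitute as well as iron dextran, since supply determines which product is given. A general exclusion for any contraindication would go further than these documents can support, because they list none. Check the item at the existing Inclusion/Exclusion step in Figure 2, before randomization.

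Alongside this, the sponsor should state how a woman assigned to IV iron but not infused is managed and recorded, since the text is silent. No clinical rule is proposed here.

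The cost is one line in each list and one field on the eligibility eCRF, with no new visit or procedure. At most a handful of candidates would be lost. The planned sample size of 108, or 120 with loss, does not change.
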